## **4.2 METHOD OF TREATMENT ASSIGNMENT AND BLINDING**

This is an open-label (unblinded) study in which all subjects will be assigned to receive the same treatment, i.e., atezolizumab.

## **4.3 STUDY TREATMENT**

The investigational medicinal product (IMP) for this study is atezolizumab.

### **4.3.1 Formulation, Packaging, and Handling**

The atezolizumab drug product will be provided in a single-use, 20-cc USP/Ph. Eur. Type 1 glass vial as a colorless to slightly yellow, sterile, preservative-free clear liquid solution intended for IV administration. The vial is designed to deliver 20.0 mL (1200 mg) of atezolizumab solution, but may contain more than the stated volume to enable delivery of the entire 20.0 mL volume. The atezolizumab drug product is formulated as 60 mg/mL atezolizumab in 20 mM histidine acetate, 120 mM sucrose, 0.04% polysorbate 20, pH 5.8.

Atezolizumab must be refrigerated at 2°C–8°C (36°F–46°F) upon receipt until use. Atezolizumab vials should not be used beyond the expiration date provided by the manufacturer. No preservative is used in the atezolizumab drug product; therefore, each vial is intended for single use only. Vial contents should not be frozen or shaken and should be protected from direct sunlight.

For further details, see the Atezolizumab Pharmacy Manual and Investigator's Brochure.

### **4.3.2 Dosage, Administration, and Compliance**

The dose of atezolizumab in this study will be 1200 mg administered by intravenous infusion every 3 weeks (21 [ $\pm$  3] days). No other dilution of the vial contents is required out of the infusion bag dilution.

Administration of atezolizumab will be performed in a setting with emergency medical facilities and staff who are trained to monitor for and respond to medical emergencies.

For more detailed information on drug preparation, storage and administration, refer to the Atezolizumab Investigator's Brochure and Pharmacy Manual.

The initial dose of atezolizumab will be delivered over 60 ( $\pm$  15) minutes. If the first infusion is tolerated without infusion-associated AEs, the second infusion may be delivered over 30 ( $\pm$  10) minutes. If the 30-minute infusion is well tolerated, all subsequent infusions may be delivered over 30 ( $\pm$  10) minutes. For the first infusion, the patient's vital signs (heart rate, respiratory rate, blood pressures, and temperature) should be determined within 60 minutes before, during (every 15 [ $\pm$  5] minutes), and 30 ( $\pm$  10) minutes after the infusion. For subsequent infusions, vital signs will be collected within 60 minutes before the infusion, during the infusion if clinically indicated, and within 30 ( $\pm$  10) minutes after the infusion.

Patients will be informed about the possibility of delayed post-infusion symptoms and instructed to contact their study physician if they develop such symptoms.

No premedication will be allowed for the first dose of atezolizumab. Premedication may be administered for Cycles  $\geq 2$  at the discretion of the treating physician. The management of infusion-related reactions will be according to severity as follows:

- In the event that a patient experiences a mild (NCI CTCAE Grade 1) infusion-related event, the infusion rate should be reduced to half the rate being given at the time of event onset. Once the event has resolved, the investigator should continue to deliver the infusion at the reduced rate for 30 minutes ( $\pm 10$ ) minutes. If tolerated, the infusion rate may then be increased to the original rate
- In the event that a patient experiences a moderate infusion-related event (NCI CTCAE Grade 2) or flushing, fever, or throat pain, the patient should have his or her infusion immediately interrupted and should receive aggressive symptomatic treatment. The infusion should be restarted only after the symptoms have adequately resolved to baseline grade. The infusion rate at restart should be half of the infusion rate that was in progress at the time of the onset of the infusion-related event
- For severe or life-threatening infusion-related events (NCI CTCAE Grade 3 or 4), the infusion should be stopped immediately, and aggressive resuscitation and supportive measures should be initiated. Patients experiencing severe or life-threatening infusion-related events will not receive further infusion and will be further managed as clinically indicated until the event resolves

For anaphylaxis precautions, see [Appendix 6](#).

Guidelines for dosage modification, treatment interruption or discontinuation, and the management of specific adverse events are provided in Section [5.1.2](#).

Any overdose or incorrect administration of study drug should be noted on the Study Drug Administration electronic Case Report Form (eCRF). AEs associated with an overdose or incorrect administration of study drug should be recorded on the Adverse Event eCRF.

Please refer to the Pharmacy Manual for detailed instructions on drug preparation, storage and administration.

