#### ***Treatment Interruption***

Atezolizumab may be temporarily suspended in patients who experience toxicity considered to be related to study treatment. If atezolizumab is withheld for > 12 weeks, the patient will be discontinued from study drug. *Atezolizumab can be resumed after being withheld for >12 weeks if the patient is likely to derive clinical benefit. The decision to re-challenge patients with atezolizumab should be based on investigator's assessment of benefit-risk and documented by the investigator. The Medical Monitor is available to advise as needed. Atezolizumab treatment may be suspended for reasons other than toxicity (e.g., surgical procedures).* If a patient must be tapered off steroids

that have been used to treat adverse events, then atezolizumab may be withheld for more than 12 weeks from the last dose until the steroids are discontinued or reduced to a prednisone dose (or dose equivalent) of  $\leq 10$  mg/day. For patients with CNS metastases or autoimmune disease who require chronic steroid therapy, who have been receiving additional steroids to treat adverse events, and who now require a reduction in steroid dosage, atezolizumab may be withheld for more than 12 weeks from the last dose until the steroid dosage has returned to its baseline value. The investigator will determine the acceptable length of treatment interruption. The acceptable length of treatment interruption *must be based on an assessment of benefit–risk by the investigator and in alignment with the protocol requirements for the duration of treatment and documented by the investigator. The Medical Monitor is available to advise as needed.*

For the management of atezolizumab related adverse events please refer to [Appendix 11](#) and Section 6 of the latest version of the Investigator's Brochure.

For patients developing a new autoimmune disease not listed in [Appendix 11](#) and Section 6 of the latest version of the Atezolizumab Investigator's Brochure, or for patients with an autoimmune disease who develop a flare, the following dosing guidance should be applied:

- Grade 1 event: atezolizumab dosage should be maintained
- Grade 2 or 3 event: atezolizumab should be suspended until the subject responds to treatment of the autoimmune disease and the disease becomes stable (see rules above regarding maximum suspended time). The subject should be referred to an appropriate specialist

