## 6.1 DETERMINATION OF SAMPLE SIZE

This is a single-arm safety study. There is no formal statistical hypothesis and all analyses will be descriptive. The results for the primary safety variables will be presented via percentages and corresponding 95% Clopper-Pearson CIs.

A sample size of approximately 1000 patients is planned for this study. The precision of rare AE incidence estimates presented by two-sided exact 95% Clopper-Pearson CIs are shown in [Table 6](#).

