#### **TREATMENT INTERRUPTION**

Atezolizumab treatment may be temporarily suspended in patients experiencing toxicity considered to be related to study treatment. If corticosteroids are initiated for treatment of the toxicity, they must be tapered over  $\geq 1$  month to  $\leq 10$  mg/day oral prednisone or equivalent before atezolizumab can be resumed. If atezolizumab is withheld for  $> 12$  weeks after event onset, the patient will be discontinued from atezolizumab. However, atezolizumab may be withheld for  $> 12$  weeks to allow for patients to taper off corticosteroids prior to resuming treatment. Atezolizumab can be resumed after being withheld for  $> 12$  weeks if the patient is likely to derive clinical benefit. *The decision to re-challenge patients with atezolizumab should be based on investigator's assessment of benefit–risk and documented by the investigator. The Medical Monitor is available to advise as needed. Atezolizumab treatment may be suspended for reasons other than toxicity (e.g., surgical procedures). The acceptable length of treatment interruption must be based on an assessment of benefit–risk by the investigator and in alignment with the protocol requirements for the duration of treatment and documented by the investigator. The Medical Monitor is available to advise as needed.*

**Appendix 11: Risks Associated with Atezolizumab and Guidelines for Management of Adverse Events Associated with Atezolizumab (cont.)**

---

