**Table 1 Management Guidelines for Infusion-Related Reactions and Cytokine-Release Syndrome**

Event	Management
Grade 1a Fever b with or without constitutional symptoms	

• Immediately interrupt infusion.

• Upon symptom resolution, wait for 30 minutes and then restart infusion at half the rate being given at the time of event onset.

• If the infusion is tolerated at the reduced rate for 30 minutes, the infusion rate may be increased to the original rate.

• If symptoms recur, discontinue infusion of this dose.

• Administer symptomatic treatment,c including maintenance of IV fluids for hydration.

• In case of rapid decline or prolonged CRS (>2 days) or in patients with significant symptoms and/or comorbidities, consider managing as per Grade 2.

• For subsequent infusions, consider administration of oral premedication with antihistamines, anti-pyretics, and/or analgesics, and monitor closely for IRRs and/or CRS.

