**Table 7 Management Guidelines for Infusion-Related Reactions and Cytokine-Release Syndrome (cont.)**

ASTCT=American Society for Transplantation and Cellular Therapy; BiPAP=bi-level positive airway pressure; CAR=chimeric antigen receptor; CPAP=continuous positive airway pressure; CRS=cytokine-release syndrome; CTCAE=Common Terminology Criteria for Adverse Events; eCRF=electronic Case Report Form; HLH=hemophagocytic lymphohistiocytosis; ICU=intensive care unit; IRR=infusion-related reaction; MAS=macrophage activation syndrome; NCCN=National Cancer Comprehensive Network; NCI=National Cancer Institute.

Note: These management guidelines have been adapted from NCCN guidelines for management of CAR T-cell-related toxicities (Version 2.2019).

- a Grading system for these management guidelines is based on ASTCT consensus grading for CRS. NCI CTCAE v4.0 should be used when reporting severity of IRRs, CRS, or organ toxicities associated with CRS on the Adverse Event eCRF. Organ toxicities associated with CRS should not influence overall CRS grading.
- b Fever is defined as temperature  $\geq 38^{\circ}\text{C}$  not attributable to any other cause. In patients who develop CRS and then receive anti-pyretic, anti-cytokine, or corticosteroid therapy, fever is no longer required when subsequently determining event severity (grade). In this case, the grade is driven by the presence of hypotension and/or hypoxia.
- c Symptomatic treatment may include oral or IV antihistamines, anti-pyretics, analgesics, bronchodilators, and/or oxygen. For bronchospasm, urticaria, or dyspnea, additional treatment may be administered as per institutional practice.
- d Low flow is defined as oxygen delivered at  $\leq 6$  L/min, and high flow is defined as oxygen delivered at  $> 6$  L/min.
- e Resumption of atezolizumab may be considered in patients who are deriving benefit and have fully recovered from the event. *The decision to re-challenge patients with atezolizumab should be based on investigator's assessment of benefit–risk and documented by the investigator (or an appropriate delegate).* For subsequent infusions, administer oral premedication with antihistamines, anti-pyretics, and/or analgesics, and monitor closely for IRRs and/or CRS. Premedication with corticosteroids and extending the infusion time may also be considered after *assessing* the benefit–risk ratio.
- f Refer to Riegler et al. (2019).

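### After a Grade 3 or 4 infusion reaction, Protocol Section 4.3.2 bars any further infusion while Appendix 11 allows re-challenge to be considered, and no text says which prevails.

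*Protocol*

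**What the plan says.** **Grade 3 or 4 infusion reactions.** Section 4.3.2 stops the infusion and then states: "Patients experiencing severe or life-threatening infusion-related events will not receive further infusion". The Appendix 11 table for infusion reactions and cytokine-release syndrome (headed Table 1 on its first page and Table 7 on its continuation) tells the site to discontinue atezolizumab permanently at both grades. Its note e then says: "Resumption of atezolizumab may be considered in patients who are deriving benefit and have fully recovered from the event", and describes premedication for the later infusions. The opening text of Appendix 11 makes the same allowance for patients who have met permanent-discontinuation criteria, in terms of immune-mediated events.

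**Lower grades.** For a mild reaction, Section 4.3.2 says "the infusion rate should be reduced to half the rate being given at the time of event onset". The Appendix 11 Grade 1 row says "Immediately interrupt infusion", then "Upon symptom resolution, wait for 30 minutes and then restart infusion at half the rate being given at the time of event onset". Section 4.3.2 grades by NCI CTCAE. Note a to the Appendix 11 table uses ASTCT grading for management and keeps NCI CTCAE v4.0 for severity on the eCRF.

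**The 12-week limit.** The limit sentence in Section 5.1.2 names no starting point. The steroid-taper exception there says "atezolizumab may be withheld for more than 12 weeks from the last dose until the steroids are discontinued". In Appendix 11, if the drug is withheld for more than 12 "weeks after event onset, the patient will be discontinued from atezolizumab". Both sections then allow treatment to resume after more than 12 weeks if clinical benefit is likely.

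**The concern.** An investigator whose patient has recovered from a severe infusion reaction, and appears to be benefiting, finds two answers to whether the drug may be given again. Section 4.3.2 closes the question and Appendix 11 leaves it open. This is a rule on re-exposure after a severe reaction, so it bears directly on patient safety.

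It also bears on what the trial reports. Infusion-related reactions are adverse events of special interest (Protocol 5.2.3, SAP 4.6.2), and adverse events leading to discontinuation or interruption are a named safety variable (Protocol 6.4). Under Section 4.3.2 every such reaction ends treatment. Under note e the same reaction can turn out to be an interruption. A re-challenge would also be a protocol deviation on one reading and permitted conduct on the other, while the plan reports major deviations (Protocol Section 6, SAP 4.2).

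**Working it through.** The documents give no statistical figure to reproduce here. The study is descriptive ("There is no formal statistical hypothesis and all analyses will be descriptive"), and the point rests on comparing text, plus one piece of arithmetic.

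**1. Grade 3 or 4**

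| | Section 4.3.2 | Appendix 11 |
|---|---|---|
| Immediate step | Stop the infusion | Discontinue permanently and contact the Medical Monitor |
| Later infusions | None | None by default |
| Exception | None stated | Re-challenge may be considered (note e) |

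The first two rows agree in effect. The third does not: a patient re-treated under note e has been given something that Section 4.3.2 rules out. If Section 4.3.2 is read as covering only the infusion in progress, the conflict over re-challenge goes away, but that section then omits the permanent discontinuation required by Appendix 11. The two need reconciling on either reading. The documents give no map between the grading scales, so this comparison assumes a patient who is Grade 3 or 4 on both.

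**2. Precedence.** Section 4.3.2 refers to 5.1.2 for interruption and discontinuation. Section 5.1.2 refers to Appendix 11 for related adverse events, and 5.3.5.1 describes Appendix 11 as holding the consolidated guidance on infusion reactions. The referrals run towards Appendix 11, but nothing states that it overrides Section 4.3.2.

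**3. Lower grades.** Appendix 11 Grade 1 is defined by fever. Section 4.3.2 places fever in its second bullet, which interrupts the infusion. For a febrile reaction the first step is therefore the same, and so is restarting at half rate. The differences are in detail:
- Section 4.3.2 waits for resolution to baseline grade. It states no 30-minute wait and no return to the earlier rate.
- Appendix 11 waits 30 minutes after symptoms resolve, and at Grade 1 allows the earlier rate again once 30 minutes at half rate are tolerated.
- A mild reaction without fever or hypoxia has an instruction in Section 4.3.2 but no clear row in the ASTCT-based table.

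**4. The 12-week clock.** The inputs are 12 weeks (5.1.2 and Appendix 11) and a dosing interval of 21 ± 3 days (4.3.2).
- Limit: 12 × 7 = 84 days.
- Longest on-schedule interval: 21 + 3 = 24 days.
- Counting from the last dose, 12 weeks ends on day 84 after that dose.
- Counting from an event that starts *d* days after the last dose, it ends on day 84 + *d*. With *d* between 0 and 24, that is day 84 to day 108.
- The clocks therefore differ by *d*, which is 0 to 24 days. The gap could be longer only if onset came after the next dose was already overdue.

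**5. Scale.** The documents give no count of Grade 3 or 4 infusion reactions. The nearest figure is one Grade 3–4 cytokine release syndrome among 310 patients in the earlier Phase II cohort (Protocol 1.3.4). If that rate applied here, 1/310 × 1000 ≈ 3 patients. This is an illustration, not an estimate of infusion-reaction frequency.

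**The case against.** The best defence is that note e permits and does not require. The default is the same in both places, so a site that never re-challenges complies with both. The referrals lead to Appendix 11, and the use of two scales is deliberate: ASTCT for management and NCI CTCAE for reporting. The primary endpoint is the incidence of treatment-emergent adverse events, which the re-challenge wording does not redefine. The SAP's adverse-event tables cover discontinuation but not interruption.

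Most of this stands, and it rules out several stronger readings:

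- *Sites cannot follow the protocol as written.* A reader might infer this, but the default can be followed everywhere. The conflict arises only when an investigator wishes to use the exception.
- *The Grade 3–4 rules are mutually exclusive.* They share the same default. Only the permission to re-challenge is opposed.
- *Grade 1 is slowed in one place and interrupted in the other.* The two quotes suggest this when read alone. Fever, which defines Appendix 11 Grade 1, is already an interruption trigger in Section 4.3.2.
- *The 12-week limits contradict each other.* The limit sentence in 5.1.2 names no clock. The last dose is named only in exceptions that allow the limit to be exceeded, and both sections let it be overridden.

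The defence does not answer the main point. A rule stated without exception and a rule with an exception cannot both govern the patient for whom the exception is being considered, and a direction of referral is not a statement of precedence.

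**Conclusion.** The point holds for re-challenge after a Grade 3 or 4 infusion reaction: it is barred in Section 4.3.2 and may be considered under Appendix 11, with no stated precedence. This is a stated safety rule giving opposite permissions, not a missing detail. The grading-scale and restart differences are secondary wording mismatches. So is the clock difference, which is 0 to about 24 days assuming onset within one on-schedule dosing interval, and which rarely binds because the limit can be overridden.

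Few patients are likely to be affected, although the documents do not allow the number to be estimated. The statistical consequence is confined to descriptive counts of discontinuations, interruptions and deviations. Sample size and the precision of the primary endpoint do not change. The case for acting is patient safety and consistent conduct across roughly 200 sites, not a threat to the analysis.

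**What to change.** Reconcile Sections 4.3.2 and 5.1.2 with the opening text, the Treatment Interruption text and the infusion-reaction table of Appendix 11, so that the protocol has:

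- one position on re-challenge after a Grade 3 or 4 infusion reaction;
- a stated grading scale for managing infusion reactions, with consistent restart details, keeping NCI CTCAE for severity on the eCRF;
- one starting point for the 12-week limit.

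Until that is done, state which section prevails. Which clinical rule to adopt is for the sponsor to decide, and this review takes no position on it.

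The cost is protocol wording in the next amendment, or a clarification letter to sites. No change to the sample size or the analysis methods is needed.

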#### **4.3.3      Investigational Medicinal Product Accountability**

*The Investigational medicinal product (IMP) required for completion of this study (atezolizumab) will be provided by the Sponsor.*

*The study site (i.e., investigator or other authorized personnel [e.g., pharmacist]) is responsible for maintaining records of IMP delivery to the site, IMP inventory at the site, IMP use by each patient, and disposition or return of unused IMP, thus enabling*

*reconciliation of all IMP received, and for ensuring that patients are provided with doses specified by the protocol.*

The study site should follow all instructions included with each shipment of IMP. The study site will acknowledge receipt of IMP supplied by the Sponsor, using the IxRS to confirm the shipment condition and content. Any damaged shipments will be replaced.

The investigator or designee must confirm that appropriate temperature conditions have been maintained during transit, either by time monitoring (shipment arrival date and time) or temperature monitoring, for all IMPs received and that any discrepancies have been reported and resolved before use of the IMPs. All IMPs must be stored in a secure, environmentally controlled, and monitored (manual or automated) area in accordance with the labeled storage conditions, with access limited to the investigator and authorized staff.

*Only patients enrolled in the study may receive IMPs, and only authorized staff may supply or administer IMPs.*

IMP will either be disposed of at the study site according to the study site's institutional standard operating procedure or returned to the Sponsor with the appropriate documentation. The site's method of IMP destruction must be agreed to by the Sponsor. The site must obtain written authorization from the Sponsor before any IMP is destroyed, and IMP destruction must be documented on the appropriate form.

Accurate records of all IMP received at, dispensed from, returned to, and disposed of by the study site should be recorded on the Drug Inventory Log.

